10.3 Irinotecan (Camptosar) – NSC #616348

For more information, please refer to the drug package insert.

Procurement

Commercial supplies. Pharmacies or clinics shall obtain supplies from normal commercial supply chain or wholesaler.

Formulation

Commercially available for injection 20 mg/mL (2 mL, 5 mL) [contains sorbitol 45 mg/mL; do not use in patients with hereditary fructose intolerance].

Preparation, Storage, and Stability

Refer to package insert for complete preparation and dispensing instructions. Store intact vials at room temperature and protect from light. Doses should be diluted in 250-500 mL D₅W or 0.9% NaCl to a final concentration of 0.12-2.8 mg/mL. Due to the relatively acidic pH, Irinotecan appears to be more stable in D₅W than 0.9% NaCl. Solutions diluted in D₅W are stable for 24 hours at room temperature or 48 hours under refrigeration at 2°C to 8°C. Solutions diluted in 0.9% NaCl may precipitate if refrigerated. Do not freeze.

Administration

Administer by I.V. infusion, usually over 90 minutes.

Drug Interactions

Cytochrome P450 Effect: Substrate (major) of CYP2B6, 3A4

Increased Effect/Toxicity: CYP2B6 and CYP3A4 inhibitors may increase the levels/effects of irinotecan. Bevacizumab may increase the adverse effects of irinotecan (e.g. diarrhea, neutropenia). Ketoconazole increases the levels/effects of irinotecan and active metabolite; discontinue ketoconazole 1 week prior to irinotecan therapy; concurrent use is contraindicated.

Decreased Effect: CYP2B6 and CYP3A4 inducers may decrease the levels/effects of irinotecan.

Ethanol/Nutrition/Herb Interactions Herb/Nutraceutical: St. John's Wort decreases therapeutic effect of irinotecan; discontinue \geq weeks prior to irinotecan therapy; concurrent use is contraindicated.

Pharmacokinetics

Distribution: V_d : 33-150 L/m²

Protein binding, plasma: Predominantly albumin; Parent drug: 30% to 68%, SN-38 (active metabolite): ~95%

Metabolism: Primarily hepatic to SN-38 (active metabolite) by carboxylesterase enzymes; SN-38 undergoes conjugation by UDP- glucuronosyl transferase 1A1 (UGT1A1) to form a glucuronide metabolite. Conversion of irinotecan to SN-38 is decreased and glucuronidation of SN-38 is increased in patients who smoke cigarettes, resulting in lower levels of the metabolite and overall decreased systemic exposure. SN-38 is increased by UGT1A1*28 polymorphism (10% of North Americans are homozygous for UGT1A1*28 allele). Patients homozygous for the UGT1A1*28 allele are at increased risk of neutropenia; initial one-level dose reduction should be considered for both single-agent and combination regimens. The lactones of both Irinotecan and SN-38 undergo hydrolysis to inactive hydroxyl acid forms.

Half-life elimination: SN-38: Mean terminal: 10-20 hours

Time to peak: SN-38: Following 90-minute infusion: ~1 hour

Excretion: Within 24 hours: urine: Irinotecan (11% to 20%), metabolites (SN-38 < 1%, SN-38 glucuronide, 3%)

Adverse Events

Consult the package insert for the most current and complete information including U.S. Boxed Warnings pertaining to severe diarrhea and severe myelosuppression.

Common known potential toxicities, > 10%:

Cardiovascular: Vasodilation

Central nervous system: Cholinergic toxicity (includes rhinitis, increased salivation, miosis, lacrimation, diaphoresis, flushing and intestinal hyperperistalsis); fever, pain, dizziness, insomnia, headache, chills

Dermatologic: Alopecia, rash

Endocrine & metabolic: Dehydration

Gastrointestinal: Late onset diarrhea, early onset diarrhea, nausea, abdominal pain, vomiting, cramps, anorexia, constipation, mucositis, weight loss, flatulence, stomatitis

Hematologic: Anemia, leukopenia, thrombocytopenia, neutropenia

Hepatic: Bilirubin increased, alkaline phosphatase increased

Neuromuscular & skeletal: Weakness, back pain

Respiratory: Dyspnea, cough, rhinitis

Miscellaneous: Diaphoresis, infection

Less common known potential toxicities, 1% - 10%:

Cardiovascular: Edema, hypotension, thromboembolic events

Central nervous system: Somnolence, confusion

Gastrointestinal: Abdominal fullness, dyspepsia

Hematologic: Neutropenic fever, hemorrhage, neutropenic infection

Hepatic: AST increased, ascites and/or jaundice

Respiratory: Pneumonia

Rare known potential toxicities, <1% (Limited to important or life-threatening):

ALT increased, amylase increased, anaphylactoid reaction, anaphylaxis, angina, arterial thrombosis, bleeding, Bradycardia, cardiac arrest, cerebral infarct, cerebrovascular accident, circulatory failure, colitis, deep thrombophlebitis, dysrhythmia, embolus, gastrointestinal bleeding, gastrointestinal obstruction, hepatomegaly, hiccups, hyperglycemia, hypersensitivity, hyponatremia, ileus, interstitial lung disease, intestinal perforation, ischemic colitis, lipase increased, lymphocytopenia, megacolon, MI, muscle cramps, myocardial ischemia, pancreatitis, paresthesia, peripheral vascular disorder, pulmonary embolus, pulmonary toxicity (dyspnea, fever, reticulonodular infiltrates on chest x-ray), renal failure (acute), renal impairment, syncope, thrombophlebitis, thrombosis, typhlitis, ulceration, ulcerative colitis, vertigo

Nursing Guidelines

If possible, check for any history of hypersensitivity reaction to any previous drug formulated with polysorbate 80.

Cholinergic symptoms of lacrimation, nasal congestion, diaphoresis, flushing, ABD cramping, and diarrhea can occur at the beginning, during, or immediately after the CPT-11 infusion. It is suggested that the patient remain in the treatment area for a minimum of one hour following the completion of the very first CPT-11 infusion. If diarrhea occurs within one hour of infusion, refer to [Section 8.1.5](#) for management.

Patient education is extremely important. Impress on the patient the importance of compliance with treatment of diarrhea management. Stress the need for prompt recognition and early intervention. Motivate the patient to report any complications immediately. The cholera-like syndrome can be unresponsive to conventional antidiarrheals and can result in severe dehydration.

Ondansetron and diphenhydramine should provide good relief from the nausea/vomiting/cramping. Avoid prochlorperazine on the day of treatment due to its association with akathisia (motor restlessness). Prochlorperazine may be taken between treatments.

Advise avoidance of excess caffeine, a GI stimulant. Avoid magnesium-based antacids such as Mylanta, Maalox, Rolaids, MOM, Mag-Ox 400, and Tylenol with antacid.

The pulmonary toxicity seen is usually manifested by dyspnea beginning 42-175 days after treatment and occurs at a cumulative dose ranging from 400-1000 mg/m² (median 750). Instruct patient to report any cough or SOB.

Patients are at risk for developing eosinophilia and will improve on steroid therapy.

Hepatic enzyme elevations have been transient and did not require intervention.

Monitor CBC closely. Leukopenia occurs primarily as neutropenia but can be severe and dose limiting. The simultaneous occurrence of grade 4 diarrhea and grade 4 neutropenia is rare but may render the patient more susceptible to polymicrobial sepsis and potentially death.

Advise patients of probable hair loss.

10.4 Leucovorin Calcium – NSC #3590

For more information, please refer to the drug package insert.

Procurement

Commercial supplies. Pharmacies or clinics shall obtain supplies from normal commercial supply chain or wholesaler.

Formulation

Commercially available:

Solution for Injection 100 mg/10mL (10mL, 30 mL)

Lyophilized Powder for Injection 50 mg, 100 mg, 200 mg, 350 mg, 500 mg

Preparation, Storage and Stability

Powder for injection: Store at room temperature of 25°C (77°F). Protect from light. Solutions reconstituted with bacteriostatic water for injection U.S.P., must be used within 7 days. Solutions reconstituted with SWFI must be used immediately. Parenteral admixture is stable for 24 hours stored at room temperature (25°C) and for 4 days when stored under refrigeration (4°C). Powder for injection: Reconstitute with SWFI or BWFI; dilute with D5W or NS for infusion. When doses > 10 mg/m² are required, reconstitute using sterile water for injection, not a solution containing benzyl alcohol.

Solution for injection: Prior to dilution, store vials under refrigeration at 2°C to 8°C (36°F to 46°F). Protect from light. Dilute in D5W or NS for infusion.

Administration

Combination therapy with fluorouracil: Fluorouracil is usually given after, or at the midpoint, of the leucovorin infusion. Leucovorin is usually administered by IV bolus injection or short (10-120 minutes) IV infusion. Other administration schedules have been used; refer to individual protocols.

Drug Interactions

Capecitabine: Leucovorin Calcium-Levoleucovorin may enhance the adverse/toxic effect of Capecitabine. Risk C: Monitor therapy

Fluorouracil (Systemic): Leucovorin Calcium-Levoleucovorin may enhance the adverse/toxic effect of Fluorouracil (Systemic). This effect is associated with the ability of leucovorin or levoleucovorin to enhance the anticancer effects of fluorouracil. Risk C: Monitor therapy

Fluorouracil (Topical): Leucovorin Calcium-Levoleucovorin may enhance the adverse/toxic effect of Fluorouracil (Topical). Risk C: Monitor therapy

Fosphenytoin: Leucovorin Calcium-Levoleucovorin may decrease the serum concentration of Fosphenytoin. Risk C: Monitor therapy

PHENobarbital: Leucovorin Calcium-Levoleucovorin may decrease the serum concentration of PHENobarbital. Risk C: Monitor therapy

Phenytoin: Leucovorin Calcium-Levoleucovorin may decrease the serum concentration of Phenytoin. Risk C: Monitor therapy

Primidone: Leucovorin Calcium-Levoleucovorin may decrease the serum concentration of Primidone. Additionally, leucovorin/levoleucovorin may decrease concentrations of active metabolites of primidone (e.g., phenobarbital). Risk C: Monitor therapy

Raltitrexed: Leucovorin Calcium-Levoleucovorin may diminish the therapeutic effect of Raltitrexed. Risk X: Avoid combination

Tegafur: Leucovorin Calcium-Levoleucovorin may enhance the adverse/toxic effect of Tegafur. This effect is associated with the ability of leucovorin or levoleucovorin to enhance the anticancer effects of fluorouracil. Risk C: Monitor therapy

Trimethoprim: Leucovorin Calcium-Levoleucovorin may diminish the therapeutic effect of Trimethoprim. Management: Avoid concurrent use of leucovorin or levoleucovorin with trimethoprim (plus sulfamethoxazole) for *Pneumocystis jiroveci* pneumonia. If trimethoprim is used for another indication, monitor closely for reduced efficacy. Risk X: Avoid combination

Pharmacokinetics

Absorption: Oral, IM: Well absorbed

Metabolism: Intestinal mucosa and hepatically to 5-methyl-tetrahydrofolate (5MTHF; active)

Bioavailability: Saturable at oral doses > 25 mg; 25 mg (97%), 50 mg (75%), 100 mg (37%)

Half-life elimination: ~ 4-8 hours

Time to peak: Oral: ~ 2 hours; IV: Total folates: 10 minutes; 5MTHF: ~ 1 hour

Excretion: Urine (primarily); feces

Adverse Events

Consult the package insert for the most current and complete information.

Dermatologic: Rash, pruritus, erythema, urticaria

Hematologic: Thrombocytosis

Respiratory: Wheezing

Miscellaneous: Allergic reactions, anaphylactoid reactions

Nursing Guidelines

Headache may occur. Advise patient that analgesics such as Tylenol may help. Instruct patient to report any headache that is unrelieved.

Observe for sensitization reaction (rash, hives, pruritus, facial flushing, and wheezing).

May potentiate the toxic effects of fluoropyrimidine (5-FU) therapy, resulting in increased hematologic and gastrointestinal (diarrhea, stomatitis) adverse effects. Monitor closely.

May cause mild nausea or upset stomach. Administer antiemetics if necessary and evaluate for their effectiveness.

10.5 5-Fluorouracil (5-FU) (Efudex, Arucil, Carac, Fluoroplex) – NSC #19893

For more information, please refer to the drug package insert.

Procurement

Commercial supplies. Pharmacies or clinics shall obtain supplies from normal commercial supply chain or wholesaler.

Formulation

Commercially available as Intravenous Solution: 500 mg/10 mL (10 mL); 1 g/20 mL (20 mL); 2.5 g/50 mL (50 mL); 5 g/100 mL (100 mL)

Preparation, Storage, and Stability

Store intact vials at room temperature and protect from light. A slight discoloration may occur with storage but usually does not denote decomposition. Dilute in 50 – 1000 mL of 0.9% NaCl or D5W. If exposed to cold, a precipitate may form; gentle heating to 60°C will dissolve the precipitate without impairing the potency. Solutions in 50 – 1000 mL 0.9% NaCl or D5W or undiluted solutions in syringes are stable for 72 hours at room temperature. Fluorouracil should not be coadministered with either diazepam, doxorubicin, daunorubicin, idarubicin, cisplatin, or cytarabine. However, fluorouracil and leucovorin are compatible for 14 days at room temperature. Fluorouracil is compatible with vincristine, methotrexate, and cyclophosphamide.

Administration

Fluorouracil may be given IV push, IV infusion. Refer to the treatment section for specific administration instructions. Avoid extravasation, may be an irritant.

Drug Interactions

Fluorouracil may increase effects of warfarin. Avoid ethanol (due to GI irritation). Avoid black cohosh.

Pharmacokinetics

Distribution: $V_d \sim 22\%$ of total body water; penetrates extracellular fluid, CSF, and third space fluids (e.g., pleural effusions and ascitic fluid)

Metabolism: Hepatic (90%); via a dehydrogenase enzyme; Fluorouracil must be metabolized to be active.

Half-life elimination: Biphasic: Initial: 6-20 minutes; two metabolites, FdUMP and FUTP, have prolonged half-lives depending on the type of tissue.

Excretion: Lung (large amounts as CO_2); urine (5% as unchanged drug) in 6 hours.

Adverse Events

Consult the package insert for the most current and complete information.

Common known potential toxicities, > 10%:

Dermatologic: Dermatitis, pruritic maculopapular rash, alopecia.

Gastrointestinal (route and schedule dependent): Heartburn, nausea, vomiting, anorexia, stomatitis, esophagitis, anorexia, diarrhea. GI toxicity (anorexia, nausea, and vomiting) is generally more severe with continuous-infusion schedules.

Emetic potential: <1000 mg: Moderately low (10% to 30%) ≥ 1000 mg: Moderate (30% to 60%)

Hematologic: Leukopenia; Myelosuppressive (tends to be more pronounced in patients receiving bolus dosing of FU). Decreased white blood cell count with increased risk of infection; decreased platelet count with increased risk of bleeding.

Local: Irritant chemotherapy.

Less common known potential toxicities, 1% - 10%:

Dermatologic: Dry skin

Gastrointestinal: GI ulceration

Rare known potential toxicities, <1% (Limited to important or life-threatening):

Cardiac enzyme abnormalities, chest pain, coagulopathy, dyspnea, ECG changes similar to ischemic changes, hepatotoxicity; hyperpigmentation of nail beds, face, hands, and veins used in infusion; hypotension, palmar-plantar syndrome (hand-foot syndrome), photosensitization. Cerebellar ataxia, headache, somnolence, ataxia are seen primarily in intracarotid arterial infusions for head and neck tumors.

Nursing Guidelines

Monitor complete blood count and platelet count. Instruct patient to report signs and symptoms of infection, unusual bruising or bleeding to the physician.

Administer antiemetics as indicated.

Diarrhea may be dose-limiting; encourage fluids and treat symptomatically.

Assess for stomatitis; oral care measures as indicated. May try vitamin E oil dabbed on sore, six times daily. Cryotherapy recommended with IV push administration.

Monitor for neurologic symptoms (headache, ataxia).

Inform patient of potential alopecia.

Those patients on continuous infusion may need instruction regarding central intravenous catheters and portable intravenous or IA infusion devices.

5FU-induced conjunctivitis is a common problem. Advise patient to report any eye soreness or redness to the healthcare team.

Photosensitivity may occur. Instruct patients to wear sun block when outdoors.

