7.1 Chemotherapy (Arm 1 and Arm 2)

7.1.1 Neoadjuvant mFOLFIRINOX

Arm 1: 8 Cycles of mFOLFIRINOX

Arm 2: 7 Cycles of mFOLFIRINOX

1 cycle = 14 days

A cycle of mFOLFIRINOX is delivered as follows*:

- **Oxaliplatin**: 85 mg/m² IV over 2 hours on day 1, followed by,
- **Irinotecan**: 180 mg/m² IV over 90 minutes on day 1, followed by,
- **Leucovorin****: 400 mg/m² IV over 2 hours on day 1, followed by,
- **5-FU*****: 2400 mg/m² IV over 46-48 hours.

* Minor variations in the timing of mFOLFIRINOX delivery due to local institutional policy are allowed so long as dose and dose modifications do not vary.

** Alternatively, leucovorin may be administered concurrently with the last 30 min of oxaliplatin, and the entire 90 minutes of irinotecan.

*** 5-FU is administered via IV infusion only; there is no bolus injection of 5-FU. White blood cell growth factor is required after completion of 5-FU, administered according to institutional procedures. See [Section 8.1.9](#) for further details.

Table 2. Neoadjuvant mFOLFIRINOX Dosing

Agent	Dose	Route	Day	ReRx
Oxaliplatin	85 mg/m ²	IV	Day 1	every 2 weeks
Irinotecan	180 mg/m ²	IV	Day 1	every 2 weeks
Leucovorin	400 mg/m ²	IV	Day 1	every 2 weeks
Fluorouracil	2,400 mg/m ²	IV	Days 1-2	every 2 weeks

See [Section 7.4](#) for restaging scan imaging requirements and [Section 7.3](#) for details on surgery.

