7.1.2 Adjuvant FOLFOX

Arm 1 or Arm 2: 4 Cycles of FOLFOX

1 cycle = 14 days

FOLFOX is to be initiated 4 to 12 weeks from date of surgery.

A cycle of FOLFOX is delivered as follows:

- **Oxaliplatin**: 85 mg/m² IV over 2 hours on day 1, followed by,
- **Leucovorin**: 400 mg/m² IV over 2 hours (Alternatively, leucovorin may be administered (via separate infusion containers) concurrently with oxaliplatin), on day 1, followed by,
- **5-FU**: 400mg/m² IV bolus, then 2400 mg/m² continuous IV over 46-48 hours.

Table 3. Adjuvant FOLFOX Dosing

Agent	Dose	Route	Day	ReRx
Oxaliplatin	85 mg/m ²	IV	Day 1	every 2 weeks
Leucovorin	400 mg/m ²	IV	Day 1	every 2 weeks
Fluorouracil	400 mg/m ² bolus then 2,400 mg/m ²	IV	Days 1-2	every 2 weeks

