10.2 Oxaliplatin (Eloxatin) – NSC #266046

For more information, please refer to the drug package insert.

Procurement

Commercial supplies. Pharmacies or clinics shall obtain supplies from normal commercial supply chain or wholesaler.

Formulation

Commercially available as:

Solution for Injection: 50 mg/10 mL (10 mL); 100 mg/20 mL (20 mL); 200 mg/40 mL (40 mL)

Lyophilized Powder for Injection: 50 mg and 100 mg

Preparation, Storage, and Stability

Refer to package insert for complete preparation and dispensing instructions. Store intact vials in original outer carton at room temperature and; do not freeze. According to the manufacturer, solutions diluted for infusion are stable up to 6 hours at room temperature or up to 24 hours under refrigeration. Oxaliplatin solution diluted with D5W to a final concentration of 0.7 mg/mL (polyolefin container) has been shown to retain >90% of its original concentration for up to 30 days when stored at room temperature or refrigerated; artificial light did not affect the concentration (Andre, 2007). As this study did not examine sterility, refrigeration would be preferred to limit microbial growth. Do not prepare using a chloride-containing solution (e.g., NaCl). Dilution with D5W (250 or 500 mL) is required prior to administration. Infusion solutions do not require protection from light.

Administration

Refer to the treatment section for specific administration instructions. Administer as IV infusion over 2-6 hours. Flush infusion line with D5W prior to administration of any concomitant medication. Patients should receive an antiemetic premedication regimen. Cold temperature may exacerbate acute neuropathy. Avoid mucositis prophylaxis with ice chips during oxaliplatin infusion.

Drug Interactions

Increased Effect/Toxicity: Nephrotoxic agents may increase oxaliplatin toxicity.

When administered as sequential infusions, observational studies indicate a potential for increased toxicity when platinum derivatives (carboplatin, cisplatin, oxaliplatin) are administered before taxane derivatives (docetaxel, paclitaxel).

Decreased Effect: Oxaliplatin may decrease plasma levels of digoxin

Pharmacokinetics

Distribution: V_d : 440 L

Protein binding: >90% primarily albumin and gamma globulin (irreversible binding to platinum)

Metabolism: Nonenzymatic (rapid and extensive), forms active and inactive derivatives

Phase: 16.8 hours

Excretion: Primarily urine (~54%); feces (~2%)

Adverse Events

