Consult the package insert for the most current and complete information. Percentages reported with monotherapy.

Common known potential toxicities, > 10%:

Central nervous system: Fatigue, fever, pain, headache, insomnia

Gastrointestinal: Nausea, diarrhea, vomiting, abdominal pain, constipation, anorexia, stomatitis

Hematologic: Anemia, thrombocytopenia, leukopenia

Hepatic: Liver enzymes increased

Neuromuscular & skeletal: Back pain, peripheral neuropathy (may be dose limiting). The most commonly observed oxaliplatin toxicity is acute and cumulative neurotoxicity, observed in patients treated at doses above 100 mg/m²/cycle. This neurotoxicity has included paresthesias and dysesthesias of the hands, feet, and perioral region as well as unusual laryngopharyngeal dysesthesias characterized by a loss of sensation of breathing without any objective evidence of respiratory distress (hypoxia, laryngospasm, or bronchospasm). OXAL neurotoxicity appears to be exacerbated by exposure to cold. Patients on this study will be counseled to avoid cold drinks and exposure to cold water or air. Should a patient develop laryngopharyngeal dysesthesia, their oxygen saturation should be evaluated via a pulse oximeter; if normal, an anxiolytic agent should be given and the patient observed in the clinic until the episode has resolved. Because this syndrome may be associated with the rapidity of OXAL infusion, subsequent doses of OXAL should be administered as a 6-hour infusion (instead of the normal 2-hour infusion).

Acute and cumulative neurotoxicities are dose limiting for OXAL. The acute neurotoxicity is characterized by paresthesias and dysesthesias that may be triggered or exacerbated by exposure to cold. These symptoms occur within hours of exposure and are usually reversible over the following hours or days. Cumulative doses of OXAL above 680 mg/m² may produce functional

impairment characterized by difficulty performing activities requiring fine sensory-motor coordination; impairment is caused by sensory rather than motor changes.

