Dose-limiting side effect can be paresthesias of hands, fingers, toes, pharynx, and occasionally cramps which develops with a dose-related frequency (> 90 mg/m²). Duration of symptoms tend to be brief (less than a week) with the first course, but longer with subsequent courses. Phase I patients have reported exacerbation of paresthesias by touching cold surfaces or exposure to cold. Advise patient of these possibilities and instruct patient to report these symptoms to the health care team. Also advise patient to refrain from operating dangerous machinery that requires fine sensory-motor coordination, if symptoms appear.

These sensory neuropathies developed after subsequent courses with increasing intensity (Grade 3 toxicity after the fourth course) and with increasing duration. In 63% of the patients tested in phase I at high doses (135-200 mg/m²), neuropathies became long-term with slow reversal over several months. Disabling walking and handwriting difficulties, as well as mouth and throat dysesthesias and laryngospasms were seen. Instruct patient to report any swallowing difficulties or gait changes.

OXAL is incompatible with NS. Flush lines with D5W prior to and following OXAL infusion.

Low back pain is a common side effect, perhaps a form of hypersensitivity reaction. Instruct patient in good body mechanics, advise light massage, heat, etc.

Laryngopharyngeal dysesthesia (LPD) occurs in about 15% of patients and is acute, sporadic, and self-limited. It usually occurs within hours of infusion, is induced or exacerbated by exposure to cold, and presents with dyspnea and dysphagia. The incidence and severity appear to be reduced by prolonging infusion time. Instruct patient to avoid ice and cold drinks the day of infusion. If \geq Grade 2 laryngopharyngeal dysesthesia occurs during the administration of OXAL, do the following:

- Stop OXAL infusion
- Administer benzodiazepine and give patient reassurance
- Test oxygen saturation via a pulse oximeter
- At the discretion of the investigator, the infusion can be restarted at 1/3 the original rate of infusion.
- Rapid resolution is typical within minutes to a few hours. Can recur with retreatment.

Comparison of the Symptoms and Treatment of Laryngopharyngeal Dysesthesias and Platinum Hypersensitivity Reactions		
Clinical Symptoms	Laryngopharyngeal Dysesthesias	Platinum Hypersensitivity
Dyspnea	present	present
Bronchospasm	absent	present
Laryngospasm	absent	present
Anxiety	present	present

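### Section 10.5 recommends cryotherapy with IV push 5-FU without exempting oxaliplatin days, when Section 10.2 tells patients to avoid ice

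*Combined protocol and SAP*

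**What the plan says.** Section 10.5 (5-Fluorouracil, Nursing Guidelines) advises assessing for stomatitis and giving oral care, then adds "Cryotherapy recommended with IV push administration". It does not define cryotherapy and sets no condition on other drugs given that day.

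Section 10.2 (Oxaliplatin) deals with cold in three places:

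- Administration: "Avoid mucositis prophylaxis with ice chips during oxaliplatin infusion".
- Adverse Events: "Patients on this study will be counseled to avoid cold drinks and exposure to cold water or air". This is a study-wide counsel with no time window, and it does not name ice.
- Nursing Guidelines, on laryngopharyngeal dysesthesia: "It usually occurs within hours of infusion, is induced or exacerbated by exposure to cold, and presents with dyspnea and dysphagia". The next instruction but one is "Instruct patient to avoid ice and cold drinks the day of infusion".

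The schedule comes from Section 7.1. For neoadjuvant mFOLFIRINOX, Section 7.1.1 says "5-FU is administered via IV infusion only; there is no bolus injection of 5-FU". For adjuvant FOLFOX, Section 7.1.2 gives oxaliplatin over 2 hours on day 1, then leucovorin over 2 hours, then 5-FU as "400mg/m² IV bolus, then 2400 mg/m² continuous IV over 46-48 hours". It also allows a shorter sequence: "Alternatively, leucovorin may be administered (via separate infusion containers) concurrently with oxaliplatin".

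**The concern.** Two nursing guidelines in the same protocol address the same staff about the same visit. One recommends what is most naturally read as ice in the mouth at the 5-FU push. The other tells the patient to have no ice that day. If the push could fall on days without oxaliplatin as scheduled, the two could coexist. In this trial it does not.

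The stake is patient safety, not inference. Section 10.2 links cold to a reaction that presents with difficulty breathing and swallowing within hours of oxaliplatin, and the bolus falls inside that period. Staff who follow the 5-FU text as written would go against the oxaliplatin caution.

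**Working it through.** No statistical quantity is involved, and the plan states no figure to reproduce. The check is to lay the instructions against the day 1 schedule.

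**1. When does a 5-FU push occur?** Reading push as the bolus of Section 7.1.2:

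- mFOLFIRINOX, Arm 1: 8 cycles × 0 boluses = 0.
- FOLFOX: 4 cycles × 1 bolus = 4, each on day 1 with oxaliplatin scheduled the same day.

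So 4 of 4 scheduled pushes in a full course fall on an oxaliplatin day. Arm 2 had the same FOLFOX schedule, but Section 7.0 states that its treatment has ceased.

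**2. How long after oxaliplatin does the bolus come?** Infusion times are from Section 7.1.2. The 6-hour oxaliplatin infusion is the one Section 8.1.15 recommends after pharyngo-laryngeal dysesthesia.

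| Sequence | Oxaliplatin ends | Bolus | Gap |
|---|---|---|---|
| Leucovorin after oxaliplatin | 2 h | 2 + 2 = 4 h | 2 h |
| Leucovorin concurrent | 2 h | 2 h | about 0 h |
| 6-hour oxaliplatin, leucovorin after | 6 h | 6 + 2 = 8 h | 2 h |
| 6-hour oxaliplatin, leucovorin concurrent | 6 h | 6 h | about 0 h |

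The bolus always comes after the oxaliplatin infusion has ended, by about 0 to 2 hours, and on the same treatment day.

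**3. What does each instruction say about ice at that moment?**

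| Source | Ice at the day 1 bolus |
|---|---|
| 10.5 Nursing Guidelines | Recommended, reading cryotherapy as oral ice |
| 10.2 Administration | Not barred: the restriction ends with the infusion |
| 10.2 Adverse Events | Cold drinks and cold exposure discouraged; ice not named |
| 10.2 Nursing Guidelines | Barred for the day |

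The direct conflict is between the first row and the last.

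**4. Is it resolved elsewhere?** Section 10.5 refers to the treatment section for administration, but Section 7.1.2 is silent on cryotherapy. So are the supportive-care rules in Section 8.1, including neurologic toxicity (8.1.15), and the mucositis rules (8.2.2.3). No section says which instruction governs.

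**5. When does the conflict not arise?** Section 8.2.1 lets the drugs be modified independently, Section 8.2.2.4 stops oxaliplatin for grade 3 or 4 neurotoxicity, and Section 8.2.2.7 allows a responsible drug to be omitted. If 5-FU continues on a day without oxaliplatin, cryotherapy at the bolus does not meet the day-of-infusion restriction.

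**The case against.** The strongest reply is that the protocol, read as a whole, already points one way. Section 10.5 is generic single-drug text: its title lists topical brand names, and it mentions intracarotid infusions. No treatment section orders cryotherapy. Section 10.2 carries both a drug-specific caution and a counsel addressed to patients on this study, and these would ordinarily prevail over a generic recommendation. Cryotherapy is also undefined, so the conflict depends on reading it as oral ice. Section 10.2 describes the reaction as transient and resolving without lasting effect, and gives management steps.

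Most of this stands, and it keeps the severity low. Nothing in the documents shows that a nurse is likely to act on Section 10.5 alone. It does not remove the point: the reader has to supply the precedence, and the two sentences sit under the same kind of heading for the same staff.

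A reader might also infer that Section 10.2 contradicts itself, since one sentence covers the infusion and another the whole day. The documents do not support that. The windows are nested, so keeping to the day-long rule satisfies the shorter one. The infusion-only sentence, taken alone, is compatible with ice at the later bolus, so the conflict rests on the day-of-infusion sentence.

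**Conclusion.** The point holds as a low-severity safety inconsistency. Section 10.5 lacks an exception for oxaliplatin days, and as scheduled that omission puts it at odds with the Section 10.2 nursing guidelines at every 5-FU push. The conclusion assumes that cryotherapy means oral ice and that push means the FOLFOX bolus. Both are natural readings, though the text does not spell them out.

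A reader might be tempted to turn planned accrual and four FOLFOX cycles into a number of patients put at risk. That would count scheduled doses, not uses of ice, and still less harm. Section 10.2 puts laryngopharyngeal dysesthesia at about 15% of patients, but that is a background frequency, not the effect of ice at the bolus. No harm rate can be derived. The primary endpoint, the interim rule and the final rule are untouched.

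**What to change.** In Section 10.5, keep the cryotherapy sentence and add a clause at its end: *except on days oxaliplatin is given (see Section 10.2)*. Tying the exception to whether oxaliplatin is given that day handles holds, omissions and discontinuations without further text. Deleting the recommendation altogether would go too far, because it would also remove a stomatitis measure on bolus days without oxaliplatin, where there is no conflict.

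Optionally, change the ice-chip sentence under Administration in Section 10.2 so that it covers the day of the oxaliplatin infusion and not only the infusion itself. This is harmonisation, not correction.

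The editorial cost is one clause, or two short edits with the optional change. The clinical cost is no ice prophylaxis for stomatitis on oxaliplatin days, which is day 1 of every FOLFOX cycle as scheduled. The Section 10.2 nursing guidelines already imply that loss, and the other oral care measures in Section 10.5 remain available.
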